6.2. Describing the Study Population

Demographics and baseline data will be compared between the groups randomized to NNC or VLNC cigarettes. This will include the following: demographic characteristics (age, sex, race, ethnicity, education), tobacco use history (e.g. cigarettes per day, menthol status, vaping frequency, other tobacco product use), TLFB and nicotine dependence (PATH, total score on FTND), etc. Continuous covariates will be summarized by the mean, standard deviation, median and range and compared by two-sample tests (t-test or Wilcoxon rank sum test). Categorical covariates will be summarized by frequencies and percentages and compared using the Chi-squared test or Fisher's exact test, as appropriate.

6.3. Primary Endpoint Analysis

The primary endpoint is the total number of puffs of their study cigarette taken at each of the 5 laboratory sessions. The participant can have up to 20 puffs on the cigarette and, therefore, the result is an integer that ranges from 0 to 20.

6.3.1. Primary Analysis

Descriptive statistics will summarize the number of cigarette puffs by cigarette group and by session. Results will be presented in tabular and graphical format. The primary statistical model will be a linear mixed model (2) carried out according to the 2 x 2 x 2 design, where the between-subject factor is NNC or VLNC cigarettes and the two within-subject factors relate to e-cig flavor (cigarette or non-cigarette flavors) and nicotine content (very low or moderate). The session where no e-cigs are included will be analyzed separately by comparing the normal and reduced nicotine cigarettes groups using linear regression adjusting for baseline CPD from TLFB to improve precision. Sandwich standard

errors will be used to account for potential heteroscedasticity. Data from the four sessions where e-cigs are available will be analyzed using a linear mixed model to account for potential correlation between repeated measures on an individual. The mixed model for the balanced factorial design will allow for the evaluation of the three main effects and their interactions. The major concern for this approach is the occurrence of non-constant variance for the number of cigarette puffs. Therefore, sensitivity analysis will be performed to evaluate the robustness of our assumptions. A generalized estimating equation (GEE) model uses sandwich estimators and thus is less affected by unequal variances, however, is more negatively impacted by the occurrence of missing observations. Additionally, a negative binomial regression approach will check if modeling the number of puffs as count variables provides a better fit to the data. The first mixed model will assume that participant characteristics are balanced between groups due to randomization and include only the three main effects and their interactions along with the stratification variables (gender, menthol status, and CPD [continuous, from the BL TLFB]) and the number of cigarette puffs from session 1 to increase precision.

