3.1. Randomization

Randomization will be done in two stages. In the first stage, each individual will be randomized in a 1:1 ratio to either the normal nicotine content (NNC) or the very low nicotine content (VLNC) cigarettes in a double blinded fashion. The randomization will be stratified by gender, menthol status and cigarettes per day (<9, 9+). The goal is 60 subjects per cigarette group. The second randomization stage will be done within the subjects. Individuals in the two cigarette groups will be assigned to all four combinations of sessions involving e-cigs (flavor and nicotine content each at 2 levels) in counter balanced order, which provides 24 possible orders for the four e-cig sessions. The no e-cig session will always be first followed by the e-cig sessions, in an order randomly chosen from one of the 24 possible orders without replacement. Once all 24 session orders have been exhausted, the process will start over with another set of 24 orders. Each cigarette group (n=60) will end up with the same arrangement of the four sessions occurring 2 to 3 times. This will not allow for the evaluation of an order effect in the data analysis, but it will prevent a systematic bias due to the arrangement of the sessions.

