3.2. Sample Size

Very little has been reported in the literature on the effect of VLNC cigarettes or the dual use of e-cigarettes on adolescent smokers. To determine a reasonable effect size (ES=mean diff/common SD) for sample size calculations, we considered several recent studies investigating alternatives to usual brand cigarettes in adolescents and young adults. In the first project of the CENIC 1 center grant, cigarettes per day (CPD) at weeks 2 and 6 were recorded for adult smokers using cigarettes with the same level of nicotine planned for our current project (15.8 mg/g vs 0.4 mg/g). (Donny et al., 2015) Selecting out the youngest participants (18-24 years of age), the comparison between these two nicotine groups resulted in an ES of 0.76 at 2 weeks and 0.85 at 6 weeks. A recent study of adolescent smokers (Cassidy et al., 2015) used a very similar design as the current proposal. Participants made a series of 20 choices between puffs of their usual brand cigarettes or money, where the amount of money varied over three sessions assigned to each subject in random order (\$0.00, \$0.10, \$0.50). The ES for the comparison between 10 and 50 cents was 0.73. Therefore, based on these previous studies, we determined that 60 subjects per cigarette group would allow for the detection of an ES of 0.60 or higher with minimum statistical power of 90% for a two-sided, two-sample test where the significance level is 0.05. For the within subject comparisons defined by the 2 factors for the e-cig characteristics, an ES of 0.5 or more for the two main effects would have at least 97% power in a repeated measures analysis if the sample size is 60 per cigarette group with a significance level of 0.05. Study enrollment will continue until the number of subjects completing all 5 sessions reaches 60 in each group (120 total). Sample size and power calculations were carried out using PASS 13 (NCSS, LLC. Kaysville, Utah, 2014).

4. Study Populations

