6.1. General Approach

The primary objective of this trial is to compare the effects of VLNC and NNC cigarettes, and of the availability and characteristics of e-cigs, on preference for cigarette puffs, e-cig puffs, or puffing abstinence. The within subject factors (between sessions) will allow for the comparison of two levels of nicotine concentration in e-cigs and two categories of e-cig flavors in a 2 x 2 factorial design. Statistical analyses will be performed using SAS or R. All analyses will be completed using the intent-to-treat principle unless otherwise noted. Methods for handling missing data will be specified below. All statistical tests will be two-tailed and a p-value less than 0.05 will be considered significant for all endpoints.

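### The Session 1 regression adjusts for CPD but not for gender or menthol status, the other two stratification factors; if they predict puffs and are balanced by design, its standard error is slightly too large.

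*Combined protocol and SAP*

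**What the plan says.** SAP 3.1 covers allocation to the cigarette groups: "each individual will be randomized in a 1:1 ratio", and "The randomization will be stratified by gender, menthol status and cigarettes per day (<9, 9" or more). It does not say how balance is kept within strata, for example by blocking.

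SAP 6.3 counts cigarette puffs at all five sessions as the primary endpoint. SAP 6.3.1 then specifies two models:

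- **Session 1 (no e-cigs):** "comparing the normal and reduced nicotine cigarettes groups using linear regression adjusting for baseline CPD from TLFB to improve precision". The plan guards against unequal variances with a sandwich estimator, but does not say which type.
- **Sessions 2-5:** a linear mixed model with the three main effects and their interactions, "along with the stratification variables (gender, menthol status, and CPD [continuous, from the BL TLFB"]), plus Session 1 puffs.

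SAP 6.4 also carries the stratification factors into the secondary-endpoint models. SAP 6.3.2 offers the only other route into the Session 1 comparison. It is a secondary analysis that adds baseline covariates differing between groups at p below 0.20. The protocol's Statistical Approach has an unadjusted unequal-variance t-test for Session 1, so it does not supply the two factors either.

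**The concern.** Stratified randomisation with enforced balance removes the stratification factors from the chance variation of the arm difference. A model that omits those factors still counts their variation as residual noise. The reported standard error is then larger than the estimate's true sampling error, the confidence interval is wider than it need be, and the test rejects less often than its nominal level.

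The SAP gives no reason for treating Session 1 differently from Sessions 2-5. Its choice of gender and menthol status as strata, and their use in the mixed model for precision, suggest that its authors regard both as prognostic. SAP 6.3.2 is unlikely to close the gap, because factors balanced by design rarely differ between arms at p below 0.20. Session 1 is part of the primary endpoint and is the only session without e-cigs, so its interval will be read closely.

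**Working it through.** **Inputs from the SAP.** 60 per group and effect size 0.60 (3.2); two-sided alpha 0.05 (6.1); stratification factors (3.1); Session 1 covariates (6.3.1).

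**Assumed input.** r is the share of puff variance left after CPD that gender and menthol status explain. The documents do not give it. I use 5-10%, and show 0% and 20% as well. The effect size is taken in units of the SD left after CPD.

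**1. The plan's own figure.** SAP 3.2 says "60 subjects per cigarette group would allow for the detection of an ES of 0.60 or higher with minimum statistical power of 90"%. That figure assumes a plain comparison of two groups at two-sided alpha 0.05, with no covariates. With m = 0.60 × √(60/2) = 3.286, normal-approximation power is Φ(3.286 − 1.960) = 90.8%. The noncentral t with 118 df gives 90.3%. The figure reproduces.

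**2. Effect of the omission when strata are balanced.**

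- Overstatement of the standard error: 1/√(1−r)
- True alpha: 2 × [1 − Φ(1.960/√(1−r))]
- Power, CPD only: Φ((3.286 − 1.960)/√(1−r))
- Power, both factors added: Φ(3.286/√(1−r) − 1.960)

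| r | SE ratio | True alpha, CPD only | Power, CPD only | Power, factors added |
|---|---|---|---|---|
| 0 | 1.000 | 5.0% | 90.8% | 90.8% |
| 0.05 | 1.026 | 4.4% | 91.3% | 92.1% |
| 0.10 | 1.054 | 3.9% | 91.9% | 93.4% |
| 0.20 | 1.118 | 2.8% | 93.1% | 95.7% |

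**3. The power gap in participants.** Find the m at which the CPD-only test reaches the power in the last column.

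- r = 0.05: m = 1.960 + 1.412 × √0.95 = 3.336, so n = 2 × (3.336/0.60)² = 61.8 per group, or about 4 more in total.
- r = 0.10: m = 1.960 + 1.504 × √0.90 = 3.387, so n = 2 × (3.387/0.60)² = 63.7 per group, or about 7 more in total.

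**4. Simulation with balance enforced.** N = 120, permuted blocks of 4 in 8 strata, HC1 sandwich with t reference; 20,000 null runs and 8,000 runs at effect size 0.60 per setting. Each cell gives CPD only, then both factors added.

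| r | Alpha | Power | True SD of the estimate (null) |
|---|---|---|---|
| 0.05 | 0.046, 0.052 | 90.7%, 91.6% | 0.180, 0.180 |
| 0.10 | 0.038, 0.048 | 91.2%, 92.8% | 0.173, 0.172 |
| 0.20 | 0.030, 0.050 | 92.2%, 95.3% | 0.165, 0.164 |

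The sandwich does not remove the conservatism. The estimate itself is almost equally precise either way; it is the reported standard error that is wrong.

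**5. The same simulation with simple randomisation.** CPD-only alpha was 0.053, 0.052 and 0.050 at r = 0.05, 0.10 and 0.20. Here the estimate does lose precision: its true SD was 0.185, 0.185 and 0.184 with CPD only, against 0.182, 0.177 and 0.166 with both factors added.

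**6. Type of sandwich.** With an uncorrected HC0 estimator, simulated alpha at r = 0.05 and 0.10 was 0.047 and 0.045 with CPD only, and 0.055 and 0.059 with both factors added. Adding the factors without a small-sample correction would therefore exchange slight conservatism for slight liberality.

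**The case against.** The strongest reply is that this is small, errs on the safe side and rests on an unknown. Nothing in the documents shows that gender or menthol status predicts puffs in this task; at r = 0 there is no loss. The conservatism also needs balance within strata, and SAP 3.1 does not describe how that is achieved. SAP 6.3.1 gives the mixed model as the primary statistical model and already improves on the protocol's unadjusted t-test for Session 1. All of this stands and limits the size of the point. It does not explain why Session 1 is handled differently from the other sessions.

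A reader might infer three stronger things, none of which the documents support.

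- **That the omission throws away 5-11% of the information, or 6-13 participants.** Those figures come from 1/(1−r) − 1, which is 5.3% at r = 0.05 and 11.1% at r = 0.10, times 120. They describe the reported interval width. Under balance the estimate's true spread is virtually unchanged, and in power terms the cost is about 4-7 participants.
- **That Session 1 is the only unconfounded comparison of VLNC with NNC.** The arm contrast in Sessions 2-5 also rests on randomisation, and omitting a balanced covariate is not confounding.
- **That the planned power fails.** The 90% figure is for a two-sample test without covariates. It reproduces at 90.3-90.8%, and under balance the CPD-only model still meets it.

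**Conclusion.** The inconsistency is certain; its size is not. Two of the three stratification factors are missing from the primary Session 1 model, and no other section puts them there.

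If gender and menthol status explain 5-10% of the variance left after CPD, and allocation is balanced within strata, the reported standard error is about 3-5% too large, true alpha is about 4.4-3.9% instead of 5%, and power at effect size 0.60 is about 1 to 1.5 points lower than it could be. If balance is not enforced, alpha stays near 5% and the loss is one of precision only. If the factors are unrelated to puffs, nothing is lost.

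The test remains valid. This is a free improvement in efficiency and consistency, not the correction of an error that would mislead.

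**What to change.** In SAP 6.3.1, specify the Session 1 regression with cigarette group, gender, menthol status and continuous baseline CPD, and name a small-sample-corrected sandwich standard error (for example HC1 or HC3, with a t reference distribution). In the simulation with balanced strata, HC1 with both factors added gave alpha of 0.048-0.052.

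The cost is two degrees of freedom and a short SAP edit; the baseline data are already collected. If the finalised primary model is to stay as it is, the same regression can be added as a labelled sensitivity analysis. A line in SAP 3.1 on how balance is kept within strata would show which of the two cases above applies.

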In adolescent smokers, the only published data are on acute effects of VLNC, and those are limited. In a laboratory study comparing the effects of VLNC vs. NNC (Kassel, Evatt et al., 2007), adolescents randomized to smoke a single NNC or VLNC cigarette rated the cigarettes equal in "harshness" and "strength" but found the VLNC less "pleasant" than the NNC cigarette. Adolescents in both conditions reported reductions in negative affect from pre to post smoking, but this reduction was greater in the NNC condition than in the VLNC condition; a secondary analysis showed some compensatory smoking (i.e., greater number of puffs per cigarette) in the VLNC condition (Kassel, Greenstein et al., 2007). Cigarette effects were moderated by baseline nicotine dependence severity such that those with high dependence in the NNC condition reported the largest pre- to post-smoking decrease in negative affect, compared with all other conditions. Kassel and colleagues highlighted the value of laboratory studies for studying causal mechanisms involved in adolescent smoking; this and other laboratory studies (Bidwell et al., 2012; [name] et al., 2010) have provided strong support for negative reinforcement (smoking for relief of negative affect, craving, and other effects of withdrawal) as an important factor maintaining smoking among adolescents. Although VLNC cigarettes appear to acutely provide some withdrawal relief in adolescent smokers, they may be less effective than NNC cigarettes, suggesting that a reduced-nicotine standard for cigarettes may lead to adolescents' seeking alternative nicotine products. Furthermore, tendency to use alternative nicotine products may be moderated by level of dependence or heaviness of smoking.

Reducing the nicotine content of combusted products: the role of e-cigarettes

VLNC studies to date have not manipulated other tobacco/nicotine product use or availability, so we do not know the effects of nicotine reduction on smoking in the context of other products. But if the appeal of and reinforcement from reduced nicotine content combusted products is low, smokers will likely seek alternative sources of nicotine that may partially substitute for cigarettes. In addition to delivering

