the effects of VLNC are influenced by the concurrent availability of e-cigs varying in **nicotine concentration and flavors**. These procedures involve a sampling phase, in which the participant samples and rates the two options, followed by choice (preference) phase, consisting of a series of discrete trials in which the participant can choose between the two options (or choose to forgo either option). The option that is chosen more often is considered to have greater relative reinforcing efficacy (Comer et al., 2008). In addition to having strong internal and predictive validity (Carter et al., 2009), choice procedures have ecological validity as they mimic situations in which smokers choose which product to buy or use among those concurrently available in the natural environment. We considered a free-access procedure in which both options are made concurrently available and *ad libitum* consumption is measured, however choice procedures are generally more sensitive than free access procedures to differences among reinforcers (e.g., Griffiths et al., 1986; Shahan et al., 1999). Participants will complete **six sessions**, including the **Screening/Baseline (BL)** session, during which eligibility will be confirmed and background questionnaires will be completed. Participants will then complete five lab sessions, a minimum of 48 hours apart; each session will follow overnight smoking abstinence.

In **Lab Session 1**, only combusted cigarettes (either NNC or VLNC) will be available. This session will always occur first because, conceptually, the no-e-cig session is the baseline condition in this study; scheduling this session first ensures that smoking choices in this condition will not be affected by any potential carryover effects of e-cig exposure on smoking choices. During the sampling phase of the choice procedure ("Preference Task"), participants will sample and then rate the cigarette using the Product Rating forms. In the preference phase, participants will be prompted via computerized instructions to make a series of 10 choices. Each choice will be to either take 2 cigarette puffs or to abstain from puffing; a total of 20 cigarette puffs is available. After completing the choice task, participants will practice using the vaping devices and sample the e-liquid flavors available. They will select which cigarette and non-cigarette flavored e-liquids they want to use during Sessions 2-5.

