- 2) **Spot urine sample for smoking biomarker assessment:** Participants will be asked to provide a urine sample while in the lab to assess baseline total nicotine equivalents (TNEs). Samples will be stored at temperatures no more than -20°C. Urine samples will be sent regularly to be analyzed and stored at the University of Minnesota.

Researchers will complete the End of Visit Evaluation Form, which will be entered into REDCap.

Lab Session 1 Procedures

Participants will return for Lab Session 1 approximately one week after their screening visit. Session 1 scheduling window is a minimum of three days and maximum of 21 days later. Outside of this window, study staff should seek approval from the PI or Project Coordinator. Participants will arrive at each session having abstained from smoking sufficiently to achieve a breath CO level that is \leq 5 ppm or \leq 50% below the CO level obtained at screening/baseline.

During the Lab Session 1, participants (N=120) will be randomized equally into one of two experimental conditions (VLNC or NNC cigarettes). Participants will be assigned a cigarette that matches their menthol preference.

Physiological measures collected, recorded on paper, and entered into REDCap by the interviewer at the end of the visit:

- 1) CO (must be \leq 5 ppm or \leq 50% below the CO level obtained at screening/baseline to begin session)
- 2) Blood Pressure
- 3) Heart Rate
- 4) Urinary pregnancy test, if applicable

The following assessments will be administered as an interview and entered into REDCap by the interviewer:

- 1) Concomitant Medications Form
- 2) Health Changes Questionnaire, which will assess any health changes since the previous session
- 3) Adverse Event Form, if applicable, will assess the nature, severity, duration, action taken, and outcome of an adverse event.
- 4) TLFB Questionnaire

PRE-TASK assessments will be administered using Qualtrics or REDCap:

- 1) MNWS
- 2) QSU-10 Usual Brand Version
- 3) PANAS

Sampling Phase Procedures

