In the *Sampling Phase* (~20 min), participants will be oriented to task procedures and shown the products available for that session. In Lab Session 1, only one product - NNC or VLNC cigarettes - will be available. Once the task begins, all instructions will be delivered via computer; sessions will be continuously observed by a research assistant through a one-way mirror. Participants will be prompted via computerized instructions to take four timed puffs of the cigarette and then complete the Product Rating forms (see description below). There will be a 15-min delay prior to the *Preference Phase*. During protocol breaks, participants will be allowed to watch TV or read magazines.

Product Rating Forms will be administered using Qualtrics or REDCap immediately after sampling the product:

- 1) MNWS
- 2) QSU-10 Usual Brand Version
- 3) PANAS
- 4) CES- Study Cigarette Version
- 5) PHRS- Study Cigarette Version
- 6) Cigarette Purchase Task –Study Cigarette Version

Preference Phase Procedures

After the *Sampling Phase* has been completed, participants will complete the *Preference Phase* (30 min), which is designed to determine the relative reinforcement value of each product. During this phase, participants undergo a series of 10 choice trials, each lasting 1 minute, with a 2-min inter-trial interval. During each trial, participants will be presented (via computer) with a choice between taking 2 puffs of the cigarette or to abstain from puffing. Indices derived from this task include: total number of cigarette puffs; and total number of choices to abstain from product use. The maximum puffing rate for this task is 20 puffs in 30 minutes.

POST-TASK Physiological measures collected, recorded on paper, and entered into REDCap by the interviewer at the end of the visit:

- 1) CO

Vaping Device Practice

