Demographics and baseline data will be compared between the groups randomized to NNC or VLNC cigarettes using t-tests and chi-square tests. The endpoints of interest are the number of puffs from cigarettes, the number of puffs from e-cigs, and the number of choices to abstain from both cigarettes and e-cigs. Descriptive statistics will summarize the data by cigarette group and by session. Results will be presented in tabular and graphical format.

The **primary aim** is to examine the effects of cigarette nicotine content, e-cig nicotine concentration and e-cig flavor on choices to smoke. The primary outcome measure is the number of cigarette puffs, and the secondary outcomes are the number of e-cig puffs, and CO boost.

The **secondary aim** is to examine the effects of these factors on product appeal and sensory effects (Cigarette/E-Cig Evaluation Scale), perceived health risks (Perceived Health Risks Assessment), and pre- to post-use changes in craving (QSU), withdrawal symptoms (MNWS), and affect (PANAS). The primary statistical model to test both aims will be a linear mixed model carried out according to the $2 \times 2 \times 2$ design, where the between-subject factor is NNC or VLNC cigarettes and the two within-subject factors relate to e-cig flavor (cigarette or non-cigarette) and nicotine concentration (very low or moderate). The session where no e-cigs are included will be analyzed separately by comparing choices for NNC vs. VLNC cigarettes using a two sample t-test with unequal variances. The mixed model for the balanced factorial design will allow for the evaluation of the three main effects and their interactions. The major concern for this

approach is the occurrence of non-constant variance for the number of puffs of each product or the number of times abstaining as the dependent variables. Therefore, sensitivity analyses will be performed to evaluate the robustness of our assumptions. A generalized estimating equation (GEE) model uses sandwich estimators and thus is less affected by unequal variances, however, it is more negatively impacted by the occurrence of missing observations. Additionally, a negative binomial regression approach will check if modeling the number of puffs as a count variable provides a better fit to the data. The first mixed model will assume that participant characteristics are balanced between groups due to randomization and include only the three main effects and their interactions.

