6.3.2. Secondary Analysis

As a secondary analysis, the above analysis will be repeated accounting for any baseline imbalances. This will include covariates provided in Section 6.2 that differ across cigarette groups (VLNC, NNC) at baseline with a p-value less than 0.20.

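### The Sessions 2-5 primary model adjusts for session-1 cigarette puffs, an outcome of the randomised cigarette, so its VLNC-versus-NNC coefficient does not in general estimate the randomised effect

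*Combined protocol and SAP*

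**What the plan says.** SAP 6.3.1 analyses Sessions 2-5 with a linear mixed model that evaluates the three main effects (study cigarette, e-cigarette flavour, e-cigarette nicotine) and their interactions. To these it adds gender, menthol status and baseline timeline follow-back cigarettes per day (CPD), "and the number of cigarette puffs from session 1 to increase precision".

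The protocol places randomisation in Lab Session 1 Procedures: "During the Lab Session 1, participants (N=120) will be randomized equally into one of two experimental conditions (VLNC or NNC cigarettes". Its Sampling Phase text for that session adds: "In Lab Session 1, only one product - NNC or VLNC cigarettes - will be available". SAP 6.3 counts the session as outcome data: "The primary endpoint is the total number of puffs of their study cigarette taken at each of the 5 laboratory sessions". SAP 6.3.1 also compares session 1 between arms in its own regression.

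Two other statements bear on the point. The protocol (Overall Study Design) says that "conceptually, the no-e-cig session is the baseline condition in this study". Its Statistical Approach describes a first mixed model that assumes characteristics are "balanced between groups due to randomization and include only the three main effects and their interactions", with no session-1 term.

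**The concern.** A covariate can improve the precision of a randomised comparison without biasing it if treatment cannot have changed it. Session-1 puffs fail that test. They are counted after assignment, on the assigned cigarette, and the same cigarette type is used in Sessions 2-5. Conditioning on them takes out whatever part of the cigarette effect is already visible in session 1. It also compares arms among people matched on a post-randomisation outcome.

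The cigarette main effect is one of the three main effects of the primary model. The SAP analyses it by intent-to-treat and powers it as a plain two-sample comparison. Nothing in the SAP redefines it as an effect conditional on session-1 smoking.

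No stated primary or sensitivity model for cigarette puffs is said to drop the covariate. SAP 6.3.2 says that "the above analysis will be repeated accounting for any baseline imbalances", which carries it forward. The GEE, negative binomial and multiple-imputation analyses address variance, distribution and missing data.

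**Working it through.** **The plan's own figure.** SAP 3.2 gives 60 per arm, effect size 0.60, two-sided alpha 0.05 and at least 90% power. With noncentrality 0.60 × √(60/2) = 3.29 on 118 df, power is 90.3%. The figure reproduces and is not in dispute.

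**Formula.** Let d1 be the arm effect (VLNC minus NNC) on session-1 puffs, d2 the arm effect on the Sessions 2-5 mean, and b the within-arm slope of that mean on session-1 puffs given the other covariates. The adjusted arm coefficient is

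d2 - b·d1.

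The bias is zero if d1 = 0 or b = 0. The effect is partly removed if d1 and d2 share a sign, and overstated if they differ. It reverses only if b·d1 exceeds d2 in the same direction.

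**Assumptions, since the documents give neither d1 nor b.** Unit SD in each session, equal correlation ρ between all sessions, 60 completers per arm, and CPD in the model with correlation c to puffs. Then b = (ρ - c²)/(1 - c²), which is ρ when c = 0.

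**Worked cell (ρ = 0.5, c = 0, d1 = d2 = -0.60).**
- Estimate: -0.60 - 0.5 × (-0.60) = -0.30.
- Variance of the four-session mean: (1 + 3 × 0.5)/4 = 0.625. After adjustment: 0.625 - 0.25 = 0.375.
- SE: √[0.375 × (2/60 + 0.36/118)] = 0.117. Power is about 72%.
- Without the covariate: estimate -0.60, SE √(2 × 0.625/60) = 0.144, power about 98%.

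**Range, true d2 = -0.60, c = 0** (power from 10,000 simulated trials per cell; simulated means match the formula to within 0.01):

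| d1 | Estimate, ρ = 0.3/0.5/0.7 | Power |
|---|---|---|
| -0.60 | -0.42/-0.30/-0.18 | 94/71/41% |
| -0.40 | -0.48/-0.40/-0.32 | 98/93/89% |
| -0.20 | -0.54/-0.50/-0.46 | above 99% |
| +0.20 | -0.66/-0.70/-0.74 | not tabulated (effect overstated) |
| covariate omitted | -0.60 | 99.7/98.4/96% |

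**CPD correlated 0.5 with puffs.** b falls to 0.07/0.33/0.60. With d1 = d2 = -0.60 the estimates are -0.56/-0.40/-0.24 and power is >99/97/68%.

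**True d2 = 0.** With d1 = ±0.20 the false-positive rate is 8/14/29% (5/10/25% if c = 0.5), against 5% without the covariate. In the extreme case d1 = -0.60, c = 0, it is 32/71/98%.

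**Which terms move.** The 2 × 2 × 2 mixed model was fitted to one simulated data set (ρ = 0.5, SD 5 puffs, both effects -0.60 SD, that is -3.0 puffs) with and without session-1 puffs. The arm coefficient went from -3.58 to -1.95 puffs. The flavour and e-cigarette nicotine effects and all interactions were identical to four decimals.

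**The case against.** **Session 1 is the baseline by design.** The protocol does call it the baseline condition, but the reason it gives is to keep smoking choices free of e-cigarette carryover. That makes it a reference for e-cigarette availability, not a pre-randomisation measurement.

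**The coefficient could be read as a direct effect.** The SAP does not define one. It would also need no unmeasured common cause, such as dependence, of early and later puffs, and randomisation does not supply that.

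**The size is unknown and may be smaller.** This stands. Session 1 is a different task (cigarette or abstain), the count is bounded at 0-20, and a ceiling after overnight abstinence could shrink both d1 and b. If session 1 correlates only 0.2 with later sessions while those correlate 0.5-0.7 among themselves, d1 = d2 = -0.60 gives -0.48 with about 90% to 83% power. With d2 = 0 and d1 = ±0.20 the false-positive rate is then about 6%.

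**Deletion may cost more power than the table suggests.** This also stands. If 0.60 is in SDs of the four-session mean, power without the covariate is 90%. With it, and d1 = 0, power would be about 95/99/>99%. That is still the SAP's stated power.

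**The direction is not really open.** The protocol's background (Adolescents and VLNC cigarettes) reports that "a secondary analysis showed some compensatory smoking (i.e., greater number of puffs per cigarette) in the VLNC condition". That is puffs on a single cigarette, whereas here each choice is a fixed two puffs. It is weak evidence that d1 could be positive, and the argument does not depend on it.

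**Other analyses are free of the covariate.** The covariates of the GEE and negative binomial models are not stated. The number of cigarette choices, half the puff count, has a mixed model in SAP 6.5 with no session-1 term listed. That endpoint is exploratory and cannot stand in for the primary analysis.

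**Conclusion.** The concern holds. As written, the Sessions 2-5 model estimates d2 - b·d1 for the cigarette main effect, not the randomised effect that the SAP sets out to test. The conditions for no bias are unlikely to be what the plan expects: the covariate adds precision only if b is not zero, and the trial is powered for a cigarette effect of 0.60.

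The algebra rests on the documents alone. The size rests on assumed values of d1, the correlations and the SDs, and ranges from negligible to a loss of 70% of the effect (-0.60 estimated as -0.18). The harm is confined to the VLNC-versus-NNC main effect in Sessions 2-5 and to arm-specific means built on it. It must be fixed, because this contrast belongs to the primary model and no stated primary or sensitivity model is said to omit the covariate.

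**What to change.** In SAP 6.3.1, end the covariate list at baseline CPD and delete "and the number of cigarette puffs from session 1 to increase precision" from the model that tests the cigarette main effect. If more precision is wanted, pre-specify covariates already collected before randomisation, such as the FTND or dependence score and baseline vaping frequency. Any model adjusted for session 1 should be a labelled supplementary analysis.

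Optionally, model all five sessions jointly as outcomes with arm-by-session means, which also uses session-1 data from participants who drop out. With 15-24% dropout depending on session-1 puffs (an assumption), both this model and plain deletion gave -0.59 to -0.61 for a true -0.60, differing by less than 0.01 SD.

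SAP 6.4 needs a related clarification. It adjusts for baseline values without defining them, and neither e-cigarette puffs nor CO boost has a pre-randomisation value. State that only values collected before randomisation qualify and that none is entered for these two endpoints. Session-1 CO boost should not be used; screening/baseline breath CO is available if a CO covariate is wanted.

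The cost is SAP wording and some nominal precision. For ρ = 0.3/0.5/0.7 the simulated SE of the cigarette effect rises from 0.115/0.113/0.099 to 0.126/0.145/0.161 SD. If CPD correlates 0.5 with puffs, it goes from 0.087/0.100/0.093 to 0.087/0.112/0.132. Power at 0.60 is about 96% or more if the effect size is in single-session SDs, and 90% if it is in SDs of the four-session mean.
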